### 12.5.1. Pregnancy Reporting

Formal reproduction toxicology testing of KPL-301 has not yet been performed.

Female subjects of childbearing potential must therefore agree to use a highly effective and protocol-approved contraceptive method (Section 7.1) for the duration of the study (until Day 90), which is 90 days after dosing and covers 5 ½ half-lives of mavrilimumab (approximately 15 days). Regular pregnancy tests will be performed for female subjects of childbearing potential, as defined in the Schedule of Activities (Table 2).

Male subjects who have a female partner of childbearing potential must agree to use a highly effective and protocol approved contraceptive method (Section 7.1) for the duration of the study and until 16 weeks after last study drug administration under this protocol.

If a subject becomes pregnant while participating in the study, study drug dosing must be discontinued immediately.

A female subject must immediately inform the Investigator if she becomes pregnant during the study. A male subject must inform the Investigator if his female partner becomes pregnant during the study. Pregnancies occurring up to 16 weeks after last study drug administration must be reported to the Investigator. The Investigator must report all pregnancies to the Sponsor or designee immediately and no later than 24 hours of their first knowledge of the pregnancy. The Investigator should counsel the subject that it is unknown what effects study drug might have on a fetus. Monitoring of the subject should continue until conclusion of the pregnancy. The newborn should be monitored for a minimum of 6 months after birth, or longer as per local requirement.

Instances of fetal death or congenital abnormality, if brought to the attention of the Investigator at any time after cessation of the study treatment and considered by the Investigator to be possibly related to the study treatment, must be reported to the Sponsor as an SAE.

### 12.5.2. Reporting of Study Treatment Errors

Medication errors are unintentional errors in the prescribing, dispensing, administration or monitoring of a medicine while under the control of a healthcare professional, subject or consumer.

Study treatment errors and uses outside of what is foreseen in the protocol will be collected in the eCRF irrespective of whether associated with an AE/SAE and reported to Safety within 24 hours of awareness only if associated with an SAE.

### **13. STATISTICAL METHODS AND PLANNED ANALYSES**

The Phase 2 and Phase 3 parts of this study and the cohorts within each phase will be independently analyzed unless otherwise specified.

#### **13.1. Analysis Sets**

##### **13.1.1. Intent-to-Treat Analysis Set**

All randomized subjects who meet eligibility criteria will be included in the intent-to-treat (ITT) analysis set. Efficacy analyses for the Phase 3 part of the study will be based on the ITT analysis set. All ITT analyses will be based on the randomized treatment.

##### **13.1.2. Modified Intent-to-Treat Analysis Set**

All randomized subjects who meet eligibility criteria and receive study drug (ie, initiation of study drug infusion) will be included in the modified intent-to-treat (mITT) analysis set. Efficacy analyses for the Phase 2 part of the study will be based on the mITT analysis set. All mITT analyses will be based on the randomized treatment.

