##### **Modified ITT (mITT) Analysis Set:**

All randomized subjects who meet eligibility criteria and received study drug will be included in the mITT analysis set.

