### 8.4. Randomization and Blinding

#### 8.4.1. Randomization

After meeting all inclusion/exclusion criteria and obtaining informed consent, subjects will be randomized in a 1:1:1 allocation ratio to receive either a 10 mg/kg or 6 mg/kg single IV dose of mavrilimumab, or placebo.

There will be 3 stratification factors for randomization:

1. Use of authorized standard of care antiviral therapy for COVID-19 (eg, remdesivir): yes vs. no
2. Age: < 65 vs.  $\geq$  65 years
3. Acute respiratory distress syndrome (ARDS) status by  $\text{PaO}_2/\text{FiO}_2^*$ : normal-mild ( $> 200$  vs. moderate-severe ( $\leq 200$ ). ARDS status will only be used for Cohort 1 (non-ventilated subjects).

\* If  $\text{PaO}_2$  is unavailable, use  $\text{SpO}_2/\text{FiO}_2$ : normal-mild ( $> 235$ ) vs. moderate-severe ( $\leq 235$ )

An Interactive Web Response System (IWRS) will be used during the study for assignment of a Subject Identification Number at enrollment, randomization to a treatment, and assignment of blinded study drug. A subject is considered randomized into the study when the Investigator confirms the eligibility criteria in the IWRS and the pharmacist has been provided with the investigational product number.

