#### **13.2. Statistical Analysis**

This section outlines the overall methodologies. Details of the statistical analyses, methods, and data conventions will be described in the Statistical Analysis Plan (SAP).

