## History of Changes

Version Number	Version Date	Notes
1.0	November 9, 2021	Final, submitted to the FDA.
2.0	December 13, 2021	
Amendment, to be submitted to the FDA.
 
The following changes are made per FDA feedback on SAP V1.0:
 

1) As per FDA guidance, the ITT definition was reverted back to the original definition to clarify unequivocally that all randomized subjects will be in the ITT analysis set.

2) For binary endpoints, specified the CMH test stratified by randomization strata as the main method for the 95% CI. Removed the 95% CI based on normal approximation.

3) Added sensitivity analysis using multiple imputation methods to handle missing data in binary endpoints.

4) Added details for tipping point analysis and reference.

 
The definition of NIAID at randomization and Day 1 NIAID are further clarified via some editorial changes.

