### **3. ANALYSIS SETS**

#### **3.1. Modified Intent-to-Treat (mITT) Analysis Set**

All randomized subjects who receive study drug will be included in the mITT analysis set. All efficacy analyses of the study will be based on the mITT analysis set. All mITT analyses will be based on the randomized treatment.

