#### **4.1. Randomization, Stratification, and Blinding**

An Interactive Web Response System (IWRS) will be used for assignment of the subject identification number at enrollment, randomization to a treatment arm (10 mg/kg KPL-301, 6 mg/kg KPL-301 or placebo), and assignment of blinded investigational product.

The randomization is stratified by three characteristics of the subjects in Cohort 1 and by the first two characteristics for Cohort 2.

1. Use of approved standard of care antiretroviral therapy: yes vs. no
2. Age: <65 vs. ≥ 65 years

3. Acute respiratory distress syndrome (ARDS) status: normal – mild ( $> 200$  PaO2/FiO2) vs. moderate-severe ( $\leq 200$  PaO2/FiO2). If PaO2 is unavailable, use SpO2/FiO2: normal–mild ( $>235$  mmHg) vs. moderate-severe ( $\leq 235$  mmHg)

There should be no overlap of subject populations between the two cohorts since Cohort 1 baseline NIAID should be 3 or 4 and Cohort 2 baseline NIAID should be 2. In case of subjects being erroneously randomized under the incorrect cohort, the subjects will be analyzed in the correct cohort defined by the baseline NIAID scale. Subjects with baseline NIAID  $\geq 5$  will be included in Cohort 1 for analyses based on mITT and safety populations but excluded from per protocol analyses.

If subjects were randomized based on incorrect baseline information (strata), then the correct strata will be used for stratified analysis rather than the incorrect strata recorded at randomization.

If fewer than 5 subjects are in a stratification group of all three (or two for cohort 2) factors, that group will be pooled with another stratification group. If the same situation occurs, strata for the second factor will be pooled. If the same situation still exists, the analysis will be done without stratification.

For stratified analyses, if there is no event for both arms of comparison, or all responses are the same within a stratification group, that group will be pooled with another stratification group per the order of the stratification factors listed previously. This principal will be analogously applied to subgroups, but only to those subgroups for which lack of events/responses require it.

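### The protocol's Phase 2 mITT set excludes dosed subjects judged ineligible after randomization, the Phase 2 SAP's mITT set keeps them, and neither document reconciles the two

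*Combined protocol and SAP*

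**What the plan says.** The protocol Synopsis defines the modified ITT set as follows: "All randomized subjects who meet eligibility criteria and received study drug will be included in the mITT analysis set". Section 13.1.2 repeats the condition ("All randomized subjects who meet eligibility criteria and receive study drug (ie, initiation of study drug infusion) will be included") and gives the set its role: "Efficacy analyses for the Phase 2 part of the study will be based on the mITT analysis set". Section 13.1.1 puts the same eligibility condition on ITT. Section 13.1.4 draws the per-protocol set from mITT/ITT.

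Phase 2 SAP section 3.1 defines the same-named set differently: "All randomized subjects who receive study drug will be included in the mITT analysis set". Section 4.1 of that SAP fits this definition. Dosed subjects with a baseline NIAID score of 5 or more, who do not belong in either cohort, "will be included in Cohort 1 for analyses based on mITT and safety populations but excluded from per protocol analyses". Section 6 of the Phase 2 SAP, on changes from the protocol, does not mention the mITT set.

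For Phase 3 the same question has been settled. The Phase 3 SAP's History of Changes reports that, after FDA feedback, the ITT definition was restated "to clarify unequivocally that all randomized subjects will be in the ITT analysis set". Section 3.1 of that SAP carries the definition, and its section 6 lists it as a change from the protocol.

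**The concern.** Two documents give one name to two different populations, and that population is the primary one for Phase 2 efficacy. The protocol version conditions on a judgment made after randomization. Protocol section 8.4.1 says "A subject is considered randomized into the study when the Investigator confirms the eligibility criteria in the IWRS", so every randomized subject has already passed the check once. The condition therefore acts only on subjects whose eligibility is revised later. The protocol does not say who makes that revision, when, or whether they are blinded. The blinded deviation review in Phase 2 SAP section 4.5 decides per-protocol membership, not mITT membership.

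Removing dosed subjects in this way departs from the comparison as randomized. The protocol's sensitivity analyses cannot show the effect either, because its ITT, mITT and per-protocol sets all exclude the same subjects. What is at stake is the Phase 2 efficacy reading. Protocol section 6.1 ties continuation of Phase 3 to it, and section 13.3.2 used it to adjust the Phase 3 planning rates. The Phase 3 SAP (section 1) also covers selected outputs that pool the two phases.

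**Working it through.** **1. Which set keeps a subject who is randomized, dosed and later judged ineligible?**

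- Protocol ITT (13.1.1): no.
- Protocol mITT (13.1.2 and Synopsis): no.
- Protocol per-protocol (13.1.4, a subset of mITT/ITT): no.
- Protocol Safety (13.1.3): yes, but it is used for safety only, by treatment received.
- Phase 2 SAP mITT (3.1): yes, by randomized treatment.

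The Phase 2 SAP definition is the only Phase 2 efficacy set that keeps such a subject.

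**2. The plan's own design figures.** Inputs from protocol 13.3.1: Fisher's exact test, two-sided 0.20; Cohort 1 at 95% vs 75%, 40 per arm, 15% dropout; Cohort 2 mortality at 40% vs 80%, 17 per arm. Exact power is the sum over all tables of Bin(a; n, p1) × Bin(b; n, p2), counting tables with Fisher p ≤ 0.20.

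- Cohort 1: 40 × 0.85 = 34 evaluable per arm, power 80.6% (85.7% at the full 40).
- Cohort 2: 17 per arm, power 81.4%.

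Both agree with the stated 80%.

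**3. Effect of one subject.** One subject is 1/40 = 2.5% of a Cohort 1 arm. The counts below are illustrative and are not trial results.

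- *All dosed, 35/40 active vs 30/40 placebo.* There are 15 non-responders among 80, 5 of them active. The hypergeometric probability of 5 or fewer is 0.0841 + 0.0318 + 0.0083 + 0.0014 + 0.0001 = 0.1257. The arms are equal, so the upper tail matches and p = 0.2515 before rounding.
- *One active non-responder excluded, 35/39 vs 30/40.* There are 14 non-responders among 79, 4 of them active. Lower tail: 0.0560 + 0.0170 + 0.0033 + 0.0004 = 0.0767. Upper-tail outcomes no more likely than the observed one (10 or more): 0.0467 + 0.0133 + 0.0025 + 0.0003 = 0.0628. The sum is p = 0.1395.
- *One placebo responder excluded instead, 35/40 vs 29/39.* p = 0.161.
- *Cohort 2, deaths 9/17 active vs 13/17 placebo.* p = 0.2818; without one active death, 8/16 vs 13/17, p = 0.1571.

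**4. How often the data fall that close.** This is the probability, per comparison, that some single exclusion changes the verdict at 0.20:

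- Cohort 1, 40 vs 40: 7.1% at 95% vs 75%; 9.1% at 75% vs 75%.
- Cohort 2, 17 vs 17: 8.4% at 40% vs 80%; 14.6% at 80% vs 80%.

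These figures let the excluded subject be the one that matters most. If the one excluded Cohort 1 subject is picked at random, the verdict changes in about 2.6% of trials at 95% vs 75% and 3.2% at 75% vs 75%.

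Direction matters too. At the planned equal sizes, one exclusion can turn a non-significant result significant but never the reverse. With unequal arms it can go either way: with 39 active and 40 placebo at 95% vs 75%, 7.9% of comparisons are significant results that one exclusion could reverse.

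**The case against.** The strongest reply is that the SAP governs and already has the better definition. Protocol section 13.2 sends the details of the analysis to the SAP, and section 13.2.1 calls the protocol's text a shortened account of the SAP's populations and methods. If the Phase 2 SAP was followed, no eligibility exclusion was made. The Phase 2 Day 29 results were also in hand when the current protocol was written, so rewording it cannot change the decisions taken on them. Both points stand, and they limit the matter to consistency and reporting. They do not remove it: the protocol names its own mITT set as the Phase 2 efficacy set and states no rule of precedence for a population that differs.

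A reader might also infer more than the documents support:

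- *That the SAP made an undeclared change.* The Phase 2 SAP was written against protocol amendment 2.0, while the condition quoted here is in Amendment 5. The amendment 2.0 mITT wording is not available, so the condition may have been added later.
- *That the exclusion tipped the actual Phase 2 result.* The rates 87.5% and 74.4% match 35/40 and 29/39 (p = 0.161), and dropping one placebo non-responder gives 35/40 vs 29/38 (p = 0.245). But the documents present those rates as Phase 3 planning assumptions adjusted on Phase 2 results. They give no counts, and the flip needs a 39-subject placebo arm.
- *That crossing 0.20 would have changed the decision to continue.* The documents give 0.20 as a Type I error rate. Continuation follows a demonstration of efficacy and safety, with no p-value rule.
- *That subjects were removed after unblinding.* No section describes this.

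**Conclusion.** The definitions conflict in the current documents, and the protocol's version is the weaker one because it excludes on a post-randomization judgment in every efficacy set. The consequence is conditional. If no dosed subject was found ineligible, the two mITT sets are identical. If one was, the verdict at 0.20 could change only when the result was already close, which is about 7% to 15% of comparisons under the rates and equal arm sizes examined, and about 3% in Cohort 1 if the excluded subject is random.

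The documents report neither the number of such subjects nor which definition was used, so it cannot be said that the Phase 2 result depended on the exclusion. The Phase 3 Type I error is unaffected, because the phases are analyzed independently. This is worth correcting as an inconsistency in a primary population. It is not evidence of a biased Phase 2 finding.

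**What to change.** 1. Delete the eligibility condition from the protocol's mITT definition (Synopsis and 13.1.2), so that it matches Phase 2 SAP 3.1: all randomized subjects who receive study drug.
2. Delete it from the protocol's ITT definition (Synopsis and 13.1.1), so that it matches Phase 3 SAP 3.1: all randomized subjects.
3. Handle ineligible subjects only through the per-protocol set, where a blinded review before database lock is already planned.
4. State in the report which Phase 2 set was used, and give the number of dosed-but-ineligible subjects by arm and cohort. If that number is not zero, show the primary result with and without them.

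The cost is wording in four places and one small table. No new data are needed, and the per-protocol analysis already covers the alternative population.

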##### **13.1.3. Safety Analysis Set**

All randomized subjects receive study drug will be included in the Safety analysis set. Safety analyses will be based on the actual treatment received.

##### **13.1.4. Per-Protocol Analysis Set**

All mITT/ITT subjects without protocol deviations deemed to impact efficacy or ethical conduct will be included in the per-protocol (PP) analysis set.

#### **13.2. Statistical Analysis**

This section outlines the overall methodologies. Details of the statistical analyses, methods, and data conventions will be described in the Statistical Analysis Plan (SAP).

##### **13.2.1. General Methods**

All statistical analyses will be performed using SAS® Version 9.4 or higher. All clinical study data will be presented in subject data listings. Descriptive statistics will be presented for all endpoints and will include number of subjects (n), mean, SD, median, interquartile range, minimum and maximum for continuous variables, and frequency and percentage for categorical and ordinal variables. The final SAP will be confirmed in a separate document prior to study unblinding. An abbreviated summary of the SAP populations and methods is provided below.

##### **13.2.2. Stratified Analysis**

There will be 3 stratification factors for randomization:

1. Use of authorized standard of care antiviral therapy for COVID-19 (eg, remdesivir): yes vs. no
2. Age: < 65 vs. ≥ 65 years

3. Acute respiratory distress syndrome (ARDS) status by partial pressure of oxygen to fractional inspired oxygen ( $\text{PaO}_2/\text{FiO}_2$ ) ratio\*: normal-mild ( $> 200$ ) vs. moderate-severe ( $\leq 200$ ). ARDS status will only be used for Cohort 1 (non-ventilated subjects)

\* If  $\text{PaO}_2$  is unavailable, use  $\text{SpO}_2/\text{FiO}_2$ : normal-mild ( $> 235$ ) vs. moderate-severe ( $\leq 235$ )

When an analysis is to be stratified by these variables and a stratum has  $\leq 5$  events of interest in a log-rank test or the same response in all subjects in a Cochran-Mantel-Haenszel (CMH) test, the strata for the last stratification factor will be pooled. If the same situation occurs, strata for the second factor will be pooled. If the same situation still exists, the analysis will be done without stratification.

### 13.2.3. Handling of Dropouts and Missing Data

No dropouts will be replaced. Every effort will be made to avoid missing data. Missing data will not be imputed unless otherwise specified. For time-to-event analyses, subjects without the event will be censored. Details on handling missing data will be specified in the SAP.

### 13.2.4. Efficacy Analyses

All efficacy analyses will be based on the mITT for the Phase 2 endpoints and based on the ITT analysis set for the Phase 3 endpoints. Analyses based on other analysis sets will be considered as sensitivity analyses. All efficacy comparisons will be primarily based on each of the mavrilimumab arms versus the placebo arm.

#### 13.2.4.1. Primary Efficacy Endpoint

For the Phase 2 part of the study, the Fisher's exact test will be done for the primary efficacy endpoint for both cohorts. The CMH test adjusting for randomization strata (authorized standard of care antiviral therapy for COVID-19 [eg, remdesivir], age, and ARDS status) will be used as supportive analysis of the primary efficacy endpoint for Cohort 1.

For both cohorts in the Phase 3 part of the study, the CMH test adjusted by randomization strata (authorized standard of care antiviral therapy for COVID-19 (eg, remdesivir), age, and ARDS status) will be used to test the primary efficacy endpoint.

Number of subjects and percentages will be summarized by treatment. The 80% (for Phase 2) and 95% (for Phase 2 and 3) confidence intervals (CIs) will also be provided as appropriate.

Missing data at Day 15 will be considered as non-responder unless otherwise specified. Details for handling missing data will be specified in the SAP.

#### 13.2.4.2. Secondary and Other Efficacy Endpoints

Ventilation-free survival, overall survival, [REDACTED] time to clinical improvement, and all other time to event endpoints will be analyzed using log-rank test stratified by randomization strata. These time to event endpoints will be summarized with the 25th, 50th (median), and 75th percentiles using the Kaplan-Meier method. The 80% (for Phase 2) and 95% (for Phase 2 and 3) CIs for the percentiles will be calculated using a log-log transformation. The percentage of subjects with events and its 80% (for Phase 2) and 95% (for Phase 2 and 3) CI will

be calculated at Day 4, 8, 15, 22 and Day 29 since randomization as appropriate, using Greenwood's formula with a log-log transformation.

The hazard ratio for mavrilimumab vs. placebo and the corresponding Wald 80% (for Phase 2) and 95% (for Phase 2 and 3) CI will be calculated based on a Cox proportional-hazards model with treatment as covariate, stratified by randomization strata.

All binary endpoints in both cohorts for Phase 2 will be primarily analyzed using the Fisher's exact test. The CMH test adjusting for randomization strata (authorized standard of care antiviral therapy for COVID-19 [eg, remdesivir], age, and ARDS status) will be used as supportive analysis for Cohort 1 (non-ventilated subjects).

For the Phase 3 part of the study, the CMH test adjusted by randomization strata will be used to test all binary secondary and other efficacy endpoint for both cohorts.

#### **13.2.5. Safety Analysis**

All safety summaries will be presented for the safety analysis set. No formal statistical analysis of safety endpoints will be performed.

Descriptive statistics will be used to summarize all safety endpoints by treatment group and/or study visit. Data summaries will display parameters such as incidence of AEs, clinical laboratory variables, vital signs, body weight and body mass index, ECG parameters, and physical examinations, where available.

#### **13.2.6. Other Analyses**

Pharmacokinetic parameters of mavrilimumab will be summarized. The presence of anti-drug antibodies will be explored. Parameters of mechanical ventilation, respiratory status, SOFA/qSOFA, and health care resource utilization (eg, days and/or length in hospital/ICU) will be summarized.

#### **13.2.7. Interim Analysis**

There is no interim analysis planned for the Phase 2 or Phase 3 part of the study. Instead, the Sponsor will conduct a primary and/or final efficacy analysis (ie, review of unblinded study results) when the last subject in each Phase and Cohort completes the Day 29/Day 90 assessments.

